7.2 NULL AND ALTERNATIVE HYPOTHESES

The primary hypotheses are that BI 655066 is different than adalimumab in achieving $\geq 90\%$ reduction from baseline in the Psoriasis Area and Severity Index score (PASI 90) and sPGA score of clear(0) or almost clear(1) at Week 16 in participants with moderate to severe chronic plaque psoriasis. For the primary analyses, this study has 2 treatment arms (BI 655066 and adalimumab [refer to [Figure 3.1: 1](#)]).

- Arm 1 – Patients randomised at Visit 2 to receive 150mg BI 655066 at Randomisation (Visit 2), Week 4 and then q12 weeks
- Arm 2 – Patients randomised at Visit 2 to receive 80mg adalimumab at Randomisation (Visit 2) and then 40mg adalimumab at Week 1 and then every other week

For the second part of the trial, patients randomised to receive adalimumab at Visit 2 and achieve a PASI 50 response but not PASI 90 at Week 16 will be re-randomised to one of the following treatment arms:

Arm A – Patients re-randomised to receive BI 655066 during the remaining treatment period of the trial

Arm B – Patients re-randomised to continue to receive adalimumab during the remaining treatment period of the trial

The following null hypotheses will be tested in a hierarchical order using two-sided tests with a type I error of 0.05. The co-primary endpoints need to be significant simultaneously, therefore no alpha adjustment is necessary.

1. BI 655066 arm (Arm 1) is not different from adalimumab (Arm 2) with respect to PASI 90 or sPGA score of clear or almost clear (0 or 1) response at Week 16
2. BI 655066 arm (Arm 1) is not different from adalimumab (Arm 2) with respect to PASI 75 response at Week 16
3. BI 655066 arm (Arm 1) is not different from adalimumab (Arm 2) with respect to PASI 100 response at Week 16

For the re-randomised patients, the following null hypothesis test will be performed with a type I error of 0.05.

- BI 655066 arm (Arm A) is not different from adalimumab (Arm B) with respect to PASI 90 response at Week 44 for patients who are re-randomized at Week 16.

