Rx Day calculated relative to the first dose of study drug in Part B.

Definition of Missing Data Imputation

No global imputation is taking place at the database level. Efficacy related imputations are outlined in Section 10.0. There is no imputation for missing values in the safety analyses.

Rounding of Numeric Results

Rounding will be performed for presentation of results. No rounding will be performed before or during analyses. The ROUND function of SAS will be used to round results.

When dichotomizing continuous variables, associated continuous variables will be rounded to 9 decimal points before applying the cutoff point to determine the response status (for example, percent change from baseline in PASI score will be rounded to 9 decimal places before comparing to 90%).

The mean and median will be rounded for presentation to 1 decimal more than the data entered into the database. The standard deviation will be rounded to 2 decimal places more than the data entered into the database. The minimum and maximum values will be presented as entered into the database.

Probabilities will be rounded to 3 decimal places before assignment of statistical significance and will be presented in rounded format. Probabilities that round to zero or are reported by SAS as zero will be presented as "< 0.001." Probabilities that round to 1 or are reported by SAS as 1 will be presented as "> 0.999."

7.0 Demographics, Baseline Characteristics, Medical History, and Previous/Concomitant Medications

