10.0 Efficacy Analysis

10.1 General Considerations

The treatment effect will be evaluated based on a two-sided significance level of 0.05 (when rounded to three decimal places).

Efficacy variables will be summarized in all ITT populations. The efficacy analysis will be conducted in the ITT_A and the ITT_B_RR populations. Only the primary and ranked secondary variables will be analyzed for the per-protocol populations using primary approach to handle missing data as described below.

Subjects' actual weight category and prior TNF antagonist exposure will be used as the strata in the stratified analyses.

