10.1.1 Analyses of Categorical Variables

For categorical variables, frequencies and percentages will be summarized. The treatment groups will be compared using a Cochran-Mantel-Haenszel (CMH) test with stratification factors as strata for the analysis. The CMH test will use weights proposed by Greenland & Robins, which is calculated as follows:

$$\hat{\delta}_{MH} = \frac{\sum_{i=1}^u w_i \cdot \hat{\delta}_i}{\sum_{i=1}^u w_i}, \text{ where}$$

$$\hat{\delta}_i = \frac{x_i}{n_i} - \frac{y_i}{m_i} \text{ denotes the risk difference in stratum } i, i = 1, \dots, u$$

$$w_i = \frac{n_i \cdot m_i}{n_i + m_i} \text{ denotes the weight of stratum } i, i = 1, \dots, u$$

x_i denotes the number of patients with event in treatment₁ in stratum $i, i = 1, \dots, u$

y_i denotes the number of patients with event in treatment₂ in stratum $i, i = 1, \dots, u$

n_i denotes the number of patients on treatment₁ in stratum $i, i = 1, \dots, u$

m_i denotes the number of patients on treatment₂ in stratum $i, i = 1, \dots, u$

The estimated variance of $\hat{\delta}_{MH}$ is calculated as:

$$\widehat{var}(\hat{\delta}_{MH}) = \frac{\sum_{i=1}^u L_i}{(\sum_{i=1}^u w_i)^2}$$

where $L_i = \frac{x_i(n_i - x_i) m_i^3 + y_i(m_i - y_i) n_i^3}{n_i \cdot m_i \cdot (n_i + m_i)^2}$, $i = 1, \dots, u$

Assuming a normal distribution of $\hat{\delta}_{MH}$, an approximate 95% CI is given as follows, where $z_{0.975}$ is the 97.5% quantile of the standard normal distribution:

$$CI = \left[\hat{\delta}_{MH} \pm z_{0.975} \cdot \sqrt{\widehat{var}(\hat{\delta}_{MH})} \right]$$

Also, the approximate p-value can be calculated using the following:

$$pvalue = 2 \cdot \Pr \left[Z > \left| \frac{\hat{\delta}_{MH}}{\sqrt{\widehat{var}(\hat{\delta}_{MH})}} \right| \right], \text{ where } Z \sim N(0, 1)$$

If there is a stratum for a treatment group that has 0 subjects in any cell in the contingency table, all cells from the stratum will be added by 0.1 in order to prevent dividing by 0 in the above equations, as suggested in Greenland & Robins.

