10.2 Primary Efficacy Analysis

Primary Efficacy Analysis in Part A:

There are co-primary endpoints to assess the efficacy of risankizumab for the treatment of moderate to severe plaque psoriasis. These are as follows:

- Achievement of $\geq 90\%$ reduction from baseline PASI score (PASI 90) at Week 16
- Achievement of an sPGA of clear or almost clear (0 or 1) at Week 16

The primary null hypotheses are that risankizumab is not different from adalimumab in achieving $\geq 90\%$ reduction from baseline in the Psoriasis Area and Severity Index score (PASI 90) and sPGA of clear (0) or almost clear (1) at Week 16.

The achievement of PASI 90 at Week 16 is the first co-primary endpoint and is a binary variable with values of 0 or 1. The difference in proportion responding between treatment arms will be estimated and tested using the Cochran-Mantel-Haenszel risk difference estimate stratified by the randomization factors of baseline weight (≤ 100 kg versus > 100 kg) and prior exposure to TNF antagonists (0 versus ≥ 1).

The achievement of a sPGA of clear or almost clear at Week 16 is the second co primary endpoint and is a binary variable with values of 0 or 1. The analysis of the sPGA co-primary endpoint will be identical to that of the PASI 90 co-primary endpoint detailed above.

The co-primary endpoints of PASI 90 and sPGA clear or almost clear need to be significant simultaneously. Both endpoints compared to ADA will be tested using a two-sided test with a type I error of 0.05.

The primary analysis will be carried out in the ITT_A Population and the PP_A Population. Non-responder imputation will be used as the primary approach for missing values. LOCF and MI will be performed as sensitivity analyses.

Primary Efficacy Analysis in Part B:

The primary endpoint in Part B is the achievement of PASI 90 at Week 44 for those subjects who are re-randomized at Week 16. This endpoint will be tested independently with a type I error rate of 0.05, for the ITT_B_RR Population. A sensitivity analysis will also be performed on the same endpoint for the PP_B_RR Population.

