10.4 Handling of Multiplicity

The statistical comparisons for the primary efficacy variables and the ranked secondary variables will be carried out in the hierarchical order. This means that statistically significant results (P value ≤ 0.05) for the comparison in the higher rank (primary, then ranked secondary variables) are necessary to initiate the testing of the next comparison in the lower rank. Since a step-down procedure is used, each comparison will be tested at a significance level of 0.05 and overall alpha level of 0.05 will be preserved.

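### Rounding p-values to three decimals before an inclusive 0.05 comparison makes the working two-sided cut-off p < 0.0505, not the stated 0.05

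*SAP*

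**What the plan says.** Two statements in the SAP put rounding ahead of the decision. SAP 6.0, under the rounding conventions, says "Probabilities will be rounded to 3 decimal places before assignment of statistical significance and will be presented in rounded format", and adds that "The ROUND function of SAS will be used to round results". SAP 10.1 applies this to efficacy with a "two-sided significance level of 0.05 (when rounded to three decimal places").

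SAP 10.4 sets the direction of the cut-off. It requires "statistically significant results (P value ≤ 0.05) for the comparison in the higher rank" before the next test may start, so equality counts as significant. The same section says that "each comparison will be tested at a significance level of 0.05 and overall alpha level of 0.05 will be preserved".

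Elsewhere the level is given without qualification:

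- SAP 10.2, for the co-primary endpoints: "Both endpoints compared to ADA will be tested using a two-sided test with a type I error of 0.05".
- Protocol 7.2, for the re-randomised comparison: "the following null hypothesis test will be performed with a type I error of 0.05".

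The protocol has no rounding rule for p-values. SAP 14.1, which lists differences from the protocol, does not mention one.

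**The concern.** The operative rule is to reject when the rounded p-value is at most 0.050. That admits raw p-values above 0.05, so the nominal level exceeds the one the protocol sets and the SAP says it preserves. SAP 6.0 is also inconsistent within itself: the same block says that rounding is for presentation and that none takes place before or during analysis.

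The practical consequence is a possible conflict between test and interval. SAP 10.1.1 builds both from the same estimate and variance, and the interval uses the unrounded 97.5% normal quantile ("an approximate 95% CI is given as follows"). They should always agree. Under the rounding rule they disagree whenever p lies strictly between 0.0500 and 0.0505. A report could then carry a significance claim that its own interval does not support, and the same rounded decision would open the gate to the ranked secondary endpoints.

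**Working it through.** **1. The level implied by the rule.** Inputs: rounding to the nearest 0.001 (SAP 6.0) and an inclusive cut-off at 0.05 (SAP 10.4).

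- p = 0.05001, 0.0504 and 0.050499 all round to 0.050 and are significant. p = 0.0505 rounds to 0.051 and is not.
- The rule is therefore raw p < 0.0505. For a p-value uniform under the null, the rejection probability is 0.0505, so the stated 0.05 is not reproduced. Excess: 0.0505 − 0.0500 = 0.0005, and 0.0005/0.05 = 1%.
- Critical values: z(0.0500/2) = 1.9600; z(0.0505/2) = 1.9557.
- Both sections are needed for this result. With a strict cut-off (rounded p < 0.05) the rule would be raw p < 0.0495, z = 1.9643, which is also not 0.05.

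**2. Test against interval.** With one stratum and equal arms of n, the SAP 10.1.1 variance reduces to [x(n−x) + y(n−y)]/n³. Take x = 202, y = 179, n = 300:

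- difference = 23/300 = 0.07667
- variance = (202×98 + 179×121)/27,000,000 = 41,455/27,000,000; SE = 0.03918
- z = 0.07667/0.03918 = 1.9566; p = 0.0504, which rounds to 0.050 and is significant
- 95% CI = 0.07667 ± 1.9600×0.03918 = −0.00013 to 0.15347, which includes zero

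Enumerating all unstratified tables with the first arm higher and 0.0500 < p < 0.0505 gives 8 at 300 per arm (another is 242 against 222: p = 0.0504, CI −0.00012 to 0.13345) and none at 60 per arm. The planned test is stratified and has more possible p-values, so these tables are illustrations.

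**3. How often rounding would decide the result.** Rates and sizes come from SAP 4.3. As a check on those inputs, the usual pooled two-proportion formula (two-sided 0.05, 90% power) reproduces the sample sizes in SAP Tables 1 to 3 to within one patient per arm.

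With d = |p1−p2|/√[p1(1−p1)/n + p2(1−p2)/n], power = Φ(d−z) + Φ(−d−z):

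| Scenario | Power, unrounded | Power, rounded | Gap (points) |
|---|---|---|---|
| Part B, 70% v 40%, 60 per arm | 93.373% | 93.427% | 0.05 |
| Part B, 65% v 40%, 60 per arm | 80.846% | 80.962% | 0.12 |
| PASI 90, 70% v 50%, 300 per arm | 99.918% | 99.919% | 0.001 |
| PASI 90, 65% v 50%, 300 per arm | 96.406% | 96.439% | 0.03 |
| sPGA, 85% v 70%, 300 per arm | 99.400% | 99.407% | 0.007 |

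The largest gap at any effect size is about 0.3989 × (1.9600 − 1.9557) = 0.0017, or 0.17 points.

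**4. Stratified check for Part B.** The documents give no stratum sizes, so they are assumed here. Four layouts of 60 per arm over the four strata were simulated (10 million trials each), with the SAP's weights and its 0.1 zero-cell adjustment, and equal rates across strata within an arm. The layouts, first arm / second arm, were:

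- 35-15-7-3 / 35-15-7-3
- 36-14-7-3 / 34-16-8-2
- 30-14-11-5 / 31-13-10-6
- 44-12-3-1 / 43-13-3-1

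The gap was 0.04 to 0.05 points at 70% v 40% and 0.05 to 0.09 points at 65% v 40%. The first agrees with the table; the second is somewhat below its 0.12.

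**The case against.** The rule is pre-specified and stated openly beside the level it modifies, so nothing is hidden or post hoc. That is true, but SAP 10.1 never says that the resulting level is 0.0505, and disclosure does not reconcile it with the unqualified 0.05 elsewhere.

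The stronger objection is that the test's own approximation error is larger than the rounding effect. The exact size of the unstratified test with the SAP variance, at common rates of 40% to 70%, is 0.0521 to 0.0552 at 60 per arm, with or without rounding. At 300 per arm it moves from 0.05043 to 0.05057 at a common rate of 40% or 60%, from 0.05122 to 0.05132 at 70%, and stays at 0.0549 at 50%. This stands: removing the rounding restores the nominal level, not an exact one. It does not justify a further upward shift, and it has no bearing on the conflict between test and interval.

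It is also fair that the power gaps for single scenarios treat a discrete statistic as continuous. Unstratified, no Part B table falls in the band. The exact Part A probabilities are about 0.0005 points (70% v 50%), 0.0006 (65% v 50%) and 0.013 (85% v 70%). The zero for Part B does not carry over to the stratified test that will be used. All these figures are small.

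Finally, the co-primary endpoints must both succeed, so 0.0505 is only an upper bound there. The Part B PASI 90 test stands alone and has no such protection.

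**Conclusion.** The point holds, and it is minor. As written, the efficacy tests run at a nominal two-sided 0.0505 where the protocol and SAP state 0.05, and within a band 0.0005 wide the significance decision contradicts the SAP's own 95% confidence interval. The chance that this matters at the planning rates is about 0.05 percentage points in Part B and at most about 0.03 points in Part A.

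The conclusion rests on reading SAP 6.0, 10.1 and 10.4 together and on the inclusive sign in 10.4. The level is nominal because the tests are normal approximations on binary data. The probabilities are approximations that depend on the planning rates and, for the stratified test, on assumed stratum sizes.

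**What to change.** - **SAP 6.0:** replace the sentence that rounds before significance is assigned with: *Statistical significance is determined by comparing the unrounded p-value with 0.05; rounding to three decimals applies to presentation only.*
- **SAP 10.1:** delete the parenthesis about rounding to three decimals.
- **Display:** add an exception to the three-decimal rule in 6.0, so that any p-value that rounds to 0.050 is printed with a fourth decimal. Otherwise a non-significant 0.0504 would appear as 0.050.

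The inclusive sign in 10.4 can stay once the comparison uses the unrounded value.

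The cost is one sentence, one deletion and one display exception. By the normal approximation, power falls by about 0.05 points for Part B at 70% v 40% (93.43% to 93.37%), by 0.12 points at 65% v 40%, by 0.01 points or less for the co-primary endpoints at 70% v 50% and 85% v 70%, and by at most 0.17 points at any effect size. Sample size does not change.

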7.1 Demographic and Baseline Characteristics

Demographics and Baseline characteristics will be summarized for each arm and for overall of the ITT populations. Continuous variables will be summarized with the number of non-missing observations by mean, standard deviation, first quartile, median,

third quartile, minimum and maximum values. Categorical data will be summarized using frequencies and percentages. Statistical tests will be performed to assess the comparability of the two arms at Randomization on ITT_A and at Re-Randomization on ITT_B_RR. Per Protocol Populations will only be summarized in the accountability table. Treatment comparison will be made based on non-missing information. Continuous variables will be analyzed using one-way analysis of variance (ANOVA). Categorical variables will be analyzed using a two-sided Pearson's Chi-Square test (or an appropriate exact test if expected cell count < 5).

The following demographic and baseline parameters will be summarized.

Subject Demographics

- Sex (male, female)
- Age (years), defined as the number of years from date of birth to date of first drug
- Age categories (< 40 years, ≥ 40 – < 65 years, ≥ 65 years.)
- Race (American Indian or Alaska Native, Asian, Black or African American, Native Hawaiian or Other Pacific Islander, White, Multi Race)
- Ethnicity (Hispanic or Latino, Not Hispanic or Latino)
- Body weight (kg)
- Body weight category (≤ 100 kg, > 100 kg)
- Height (cm)
- BMI (kg/m²)
- BMI category (< 25, ≥ 25 – < 30, ≥ 30)
- Prior exposure to TNF antagonists (0 versus ≥ 1)

General Baseline Characteristics

- PASI (Psoriasis Area and Severity Index)
- BSA (Body Surface Area)
- sPGA (Static Physician Global Assessment)

- NAPSI (Nail Psoriasis Severity Index)
- PSSI (Psoriasis Scalp Severity Index)
- PPASI (Palmoplantar Psoriasis Area Severity Index)
- Dermatology Life Quality Index (DLQI)
- WLQ (Work Limitations Questionnaire)

Psoriasis and Cardiovascular History

- Psoriatic arthritis (diagnosed, suspected, no)
- Cardiovascular Diseases (myocardial infarction, angina pectoris, transient ischemic attack, stroke, deep vein thrombosis)
- Cardiovascular Risk Factors (hypertension, hyperlipidemia, diabetes mellitus, obesity)

General Use

- Smoking status (Never-smoked, Ex-smoker, Currently smokes)
- Alcohol status (Non-drinker, drinks – no interference, drinks – possible interference)

Prior Treatment

- Psoriasis Biologic Treatment History – by Response to Prior Treatment
- Psoriasis Treatment – by Therapy Type (topical therapy, phototherapy, photochemotherapy, non-biologic systemic therapy, TNF antagonist, other biologic)

Also, Physical Exam and Pregnancy Test will be presented in listing format.

7.2 Medical History

Medical history will be summarized using body systems and condition/diagnosis as captured on the eCRF. The body systems will be presented in alphabetical order and the conditions/diagnoses will be presented in alphabetical order within each body system.

The number and percentage of subjects with a particular condition/diagnosis will be summarized for each treatment arm. Subjects reporting more than one condition/diagnosis within a body system will be counted only once for that body system.

7.3 Previous Treatment and Concomitant Medications

Prior and concomitant medications will be summarized by generic name. A prior medication is defined as any medication taken prior to the first dose of study drug. A concomitant medication is defined as any medication that started prior to the first dose of study drug and continued to be taken after the first dose of study drug or any medication that started after the first dose of study drug, but not after the last dose of study drug plus 21 days. The number and percentage of subjects who had taken medications will be summarized by generic drug name assigned by the World Health Organization (WHO) for both prior and concomitant medications.

7.4 Protocol Deviations

Number and percentage of subjects who reported at least one of the following protocol deviation categories will be provided.

- Subject entered into the study even though she/he did not satisfy entry criteria
- Subject who developed withdrawal criteria during the study and was not withdrawn
- Subject who received wrong treatment or incorrect dose
- Subject who received excluded or prohibited concomitant treatment

8.0 Patient Disposition

The number of subjects for each of the following categories will be summarized, for overall and for each treatment group in the ITT_A population:

- Number of subjects randomized

- Number of subjects treated during Part A
- Number of subjects who completed Part A
- Number of subjects who discontinued study drug during Part A
- Number of subjects who prematurely discontinued from the Part A

The number of subjects for each of the following categories will be summarized, for overall and for each treatment group in the ITT_B_RR population:

- Number of subjects re-randomized
- Number of subjects treated during Part B
- Number of subjects who completed Part B
- Number of subjects who discontinued study drug during Part B
- Number of subjects who prematurely discontinued from the Part B

In addition, the reasons for premature discontinuation will be summarized with frequencies and percentages.

Disposition tables will also be summarized in the ITT_B_R, ITT_B_NR, and ITT_B_RZB Populations.

In addition to patient disposition, number of screening failures and reasons for screening failure will also be summarized among all screened subjects in a subject screening status table.

9.0 Study Drug Exposure and Compliance

Summary of study drug exposure will be provided for each treatment arm in each treatment part in the corresponding ITT populations. Study drug compliance will be summarized in ITT_A, ITT_B_RR populations.

Study drug exposure (days) will be summarized using the sample size, mean, standard deviation, minimum, median and maximum for each treatment part. In addition

cumulative exposure of RZB will be also summarized in the ALL_RZB Population.
Study drug exposure will be summarized as follows:

Study Drug Exposure (in Days) in Each Part:

Part A:

- For subjects who did not continue into Part B:
 - Date of last injection in Part A – Date of first injection in Part A + 14 days (ADA)
 - Date of last injection in Part A – Date of first injection in Part A + 84 days (RZB)
- For subjects who continued into Part B: the minimum of
 - Date of first injection in Part B – Date of first injection in Part A.
 - Date of last injection in Part A – Date of first injection in Part A + 14 days (ADA)
 - Date of last injection in Part A – Date of first injection in Part A + 84 days (RZB)

Part B:

- Date of last injection in Part B – Date of first injection in Part B + 14 days (ADA)
- Date of last injection in Part B – Date of first injection in Part B + 84 days (RZB)

ALL_RZB:

For study drug exposure during the administration of risankizumab in the ALL_RZB Population:

- Date of last injection of risankizumab – Date of first injection of risankizumab + 84 days.

Compliance

There will be a summary of the number of subjects receiving study drug and dose at each scheduled study drug administration time point for adalimumab and for risankizumab, separately. This will be repeated on the cumulative number of doses.

When computing compliance at each scheduled time point, the denominator for each week will include all subjects in each analysis population who have not prematurely discontinued study drug (or prematurely discontinued from study) prior to the scheduled study drug injection.

Self-Administration of Risankizumab Questionnaire

There will be a summary of the self-administration of risankizumab questionnaire completed by supervising nurse/health care professional.

The following items will be summarized as-observed at each visit:

- Patient able to inject all of the liquid (Yes/No)
- Reason for unable to inject all of the liquid (Unable to remove the needle cap; Unable to fully push down the plunger; Unable to empty the syringe; More than a drop of medication remained on their skin; Other)
- Injection site (Left lower abdomen; Right lower abdomen; Left thigh; Right thigh)
- Helped by supervising personnel (Yes/No)

